### ***10.2.1 Changes to Study Conduct***

If a subject is undergoing screening assessments, but cannot have protocol-required assessments performed due to COVID-19, the subject should be put on screening pause until such time as COVID-19 impacts have ceased and abstention from treatment with an AChEI and/or memantine should be retained. Screening MMSE/CDR/DV, brain scans, and G6PD blood sample collection do not require repetition if already confirmed. The approach for individual assessments is described further below. Re-screening is addressed in Section 11.3.

Both the Screening visit (including informed consent and all screening assessments) and the Baseline/Randomization visit must continue to occur in the clinic at the study site. The first dose of study drug (Visit 2) will be administered in the clinic. This visit should be scheduled to occur in the morning and subjects will be required to remain at the site for at least 4 hours post-dose.

The intervening post-Baseline visits, *i.e.*, Visits 3, 4, 5, 6 and 7 (after 4, 13, 26, 29, and 52 weeks of double-blind study drug), for clinical safety assessments (adverse event and concomitant medication recording/review), safety and PK blood sample collection (inclusive of the optional genotyping blood sample collected any time after Baseline but prior to Visit 7), as well as efficacy assessments, may be completed in-clinic at the site, in the subject's home by visiting study personnel, or at other safe, suitable alternative location, if deemed necessary to protect a subject due to COVID-19. Similarly, Visits 9 and 10 (after 26 and 52 weeks of open-label treatment) may also be completed in the clinic at the site, in the subject's home by visiting study personnel, or at other safe, suitable alternative location. Efficacy scales may also be performed remotely, if approved by the Sponsor in advance on a case-by-case basis, as further described below. The principal investigators (PIs) retain unilateral decision-making and discretion regarding ongoing subject participation dependent on local circumstance and authority recommendations. Travel to the investigational site is the subject's decision. The following procedures are also to be implemented as necessary:

- Consideration may be given on an individual site basis to expand the allowable time windows for study visits if a site closure is anticipated to be short-term.

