## 2.5. Changes of Study Conduct due to COVID-19

The protocol was revised to version 6.0 and 6.0 UK to incorporate modifications to the study conduct and monitoring, guidance for continued data collection and analysis, and ongoing risk assessment due to the Coronavirus Disease 2019 Public Health Emergency (COVID-19). Key assessments deciding the eligibility of subjects as well as Baseline, Week 52, Week 56 for UK sites, and early termination assessments must be done on-site and cannot be assessed remotely. Other visits can be done remotely as per the agreed risk assessments and data collection plans.

Since F-FDG-PET was not needed to determine study eligibility and is not the primary efficacy imaging, the Sponsor may have approved subject randomization without a brain F-FDG-PET scan if the scan could not be performed due to COVID-19. For imaging (MRI, F-FDG-PET), alternative scanners will only be accepted if data comparability is confirmed and ensured prior to assessments being made; every effort was made to avoid any change in scanner for a given site and subject over the course of the study. If a Baseline F-FDG-PET scan could not be done due to lack of imaging facility, a follow-up F-FDG-PET scan was not required.

If a subject underwent Screening assessments but could not have protocol-required assessments performed due to COVID-19, the subject could be put on screening pause until such times as COVID-19 impacts had ceased (abstention from treatment with an AChEI and/or memantine should have been retained).

The planned in-clinic post-Baseline visits (except Week 52 visit), including blood samples for safety laboratory assessments as well as optional genotyping, may have been completed at home, or at other safe, suitable alternative location if deemed necessary to protect subjects due to COVID-19.

Study visit windows may have been extended beyond the allowed +/- 14 days at the discretion of the Sponsor when justification was provided and unless two planned study visits did not fall into the same visit window as per Sections 5.5 / 6.5.

Efficacy scales may have also been performed remotely, if approved by the Sponsor in advance on a case-by-case basis.

Dose interruption not triggered by the site clinician because of COVID-19 might be allowed for more than 14 days at the discretion of the Sponsor.

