### 5.5. Visit Windows

Since data might be documented under a wrong label (as a wrong visit) within the EDC system, all data will be (re-)assigned to a visit according to the column *Intervals for analysis* in Table 5.

Furthermore, if a subject has multiple values for a parameter within a visit window, the “worst” value will be used for that visit window summary (see Appendix 12.3), for efficacy endpoints the closest to the scheduled visit will be used (if two have the same distance from the scheduled visit the later one will be used, and if two have the same day, the Sponsor will provide a file, which identifies the value to be used in the analysis). For the double-blind treatment phase, priority at Week 52 is given to assessments that took place before initiation of the open-label treatment in case there are multiple values for them within the visit window.

Sponsor:	TauRx Therapeutics Ltd.		
Protocol:	TRx-237-039		
Document Version No.:	3.0	Document Date:	07-JUN-2023

As an exception, for the analysis of the double-blind treatment phase, a delayed Week 52 F-FDG-PET or MRI assessment will be included in the double-blind treatment phase even if it has been done within 14 days after first dose of the open-label treatment phase drug. In addition, the eye exam is eligible for the double-blind treatment phase, if it was performed until the end of the Week 52 protocol-specified visit window. For all other efficacy endpoints and safety information only assessments before the first dose of the open-label treatment phase or if assessments were done on the same day of the first open-label phase treatment are eligible for analysis of double-blind treatment phase data.

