#### 5.12.3. Laboratory Data

Central laboratory data are transferred electronically by Labcorp (previously known as Covance). The Data Transfer Specification document provides a detailed description of the content and format of the laboratory datasets.

Clinical laboratory values will be reported in separate tables and listings for conventional and SI units, justified by the involvement of FDA and EMA.

The Baseline value is defined as the last non-missing value prior to first dose of study drug. Laboratory tests obtained on the date of the first dose will be assigned to pre-treatment; the relative times of blood sampling and dosing will be checked programmatically to confirm this assumption, if this is not true, the respective Screening value will be used.

The Baseline value, the actual value and change from Baseline to each on study evaluation and to the last available on-treatment value will be summarized for each clinical laboratory parameter, including hematology, and blood chemistry; restricted to subjects with at least one post-Baseline value. For continuous laboratory parameters n, Mean, Median, SD and (Min, Max) will be presented; and counts and percentages for categorical parameters. In the event of repeated values, the “worst” value per

Sponsor:	TauRx Therapeutics Ltd.		
Protocol:	TRx-237-039		
Document Version No.:	3.0	Document Date:	07-JUN-2023

study day will be used. For the hematology parameters hemoglobin and hematocrit, this descriptive analysis will be prepared separately for males and females.

Visit windows are used when results are presented by target visit (see Table 5). For each parameter, if a subject has multiple values within a visit window, the “worst” value will be used for that visit window summary (see Appendix 12.3).

Shift tables will be provided showing the change from Baseline relative to the reference range. Missing categories will be included in the shift tables.

Box-and-whisker plots and line graphs (showing the mean and standard error) of the observed data will be presented for selected parameters including hemoglobin (separately for males and females), reticulocytes, neutrophils, platelet counts, and liver function tests (ALT, AST, GGT, total bilirubin). Conventional and SI units will both be presented within each figure (as two y-axes), along with reference lines for the normal ranges. Other parameters may be identified during data review.

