#### 5.12.4. Vital Signs

The Baseline value, the actual value and change from Baseline to each on study evaluation and to the last available on-treatment value will be summarized, with the Baseline value being defined as the last non-missing value prior to first dose of study drug.

A similar summary will be generated for blood pressure values obtained on Day 1 (pre-dose and post-dose) in the subset of subjects identified as concomitantly taking the following pharmacological subgroup of serotonergic drugs at Baseline: SSRIs, SNRIs, or MAOIs (see latest version of the Serotonergic Drugs List, Section 5.8, and Section 12.4).

Sponsor:	TauRx Therapeutics Ltd.		
Protocol:	TRx-237-039		
Document Version No.:	3.0	Document Date:	07-JUN-2023

PCS vital sign changes are defined in Table 8 and will need to be calculated and identified prior to further analysis. The number and percentage of subjects meeting these criteria (any post-Baseline PCS) will be summarized according to the definition described in Section 5.12.3. Increasing and decreasing changes will be categorized separately.

Vital sign measurements will be presented in a subject data listing.

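### Safety results from a Week 52 visit held on Days 380–456, before open-label dosing, have no visit row in the double-blind by-visit tables (SAP Table 5)

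*SAP*

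**What the plan says.** SAP 5.5 re-labels every record by study day: "all data will be (re-)assigned to a visit according to the column" of analysis intervals in Table 5. In that table Week 52 covers Days 320 to 379 for safety assessments and Days 320 to 456 for ADAS-cog, ADCS-ADL and MRI. There is no later safety row.

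Phase membership is set by a different rule in the same section: "For all other efficacy endpoints and safety information only assessments before the first dose of the open-label treatment phase", or made on the day of that dose, are eligible for the double-blind analysis. This rule has no day limit.

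The windows drive the by-visit output. SAP 5.12.3 says of laboratory data: "Visit windows are used when results are presented by target visit (see Table 5"). For vital signs, SAP 5.12.4 reads: "change from Baseline to each on study evaluation and to the last available on-treatment value will be summarized, with the Baseline value being defined" (the definition it then gives is the latest pre-treatment measurement). SAP 5.12.5 summarizes examinations by visit.

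Both documents foresee late visits. SAP 2.5: "Study visit windows may have been extended beyond the allowed +/- 14 days at the discretion of the Sponsor when justification was provided". Protocol 10.2.1: "Consideration may be given on an individual site basis to expand the allowable time windows for study visits", where a site closure is expected to be short. SAP 12.1.1 states that the windows were in fact extended.

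The eye examination has its own sentence in SAP 5.5: "the eye exam is eligible for the double-blind treatment phase, if it was performed until the end of the Week 52 protocol-specified visit window".

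**The concern.** Two rules in one section do not fit together. One decides phase by the date of the first open-label dose. The other decides visit by a fixed day that, for safety, stops at the protocol limit. A subject whose Visit 7 takes place on Day 400, with blood samples, vital signs and examinations before the first open-label dose, has valid end-of-treatment safety data that the plan accepts as double-blind but gives no visit to. The cognitive and functional scores from that same visit are Week 52 scores.

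The Week 52 rows and plots for hemoglobin, other laboratory parameters, vital signs and examination findings would then omit late attenders who are present in the Week 52 efficacy results, and nothing in the plan reports the omission. Readers use the Week 52 row to judge safety at the end of the controlled period.

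**Working it through.** **Inputs.** SAP Table 5: Week 52 scheduled for Day 365, protocol interval 351 to 379, safety interval 320 to 379, efficacy and MRI interval 320 to 456. SAP Table 9: open-label Week 56 scheduled for Day 394, safety interval 380 to 470; Week 78 scheduled for Day 548. SAP 6.13.3, HMTM treatment phase: Week 52 laboratory window 274 to 456.

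**1. Reproduce the two upper limits.**
- Safety, midpoint of Weeks 52 and 56: (365 + 394)/2 = 379.5, so 379. The protocol limit is the same: 365 + 14 = 379.
- Efficacy and MRI, midpoint of Weeks 52 and 78: (365 + 548)/2 = 456.5, so 456.

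Both stated limits are reproduced.

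**2. Length of the gap.** 456 − 379 = 77 study days, Days 380 to 456.

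**3. Look up a pre-dose Visit 7 record by day.** The last column applies to subjects randomized to HMTM, for whom that table uses the double-blind study day.

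| Day | Table 5 safety | Table 5 ADAS-cog, ADCS-ADL, MRI | Table 9 safety | HMTM-phase laboratory |
|---|---|---|---|---|
| 379 | Week 52 | Week 52 | Week 52 | Week 52 |
| 380 | none | Week 52 | open-label Week 56 | Week 52 |
| 400 | none | Week 52 | open-label Week 56 | Week 52 |
| 456 | none | Week 52 | open-label Week 56 | Week 52 |
| 457 | none | none | open-label Week 56 | Week 78 |

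The break starts at Day 380. From Day 457 the efficacy scales have no double-blind row either.

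**4. Does another rule catch these values?**
- Table 9 labels them Week 56, but SAP 6.6 limits the open-label analysis to data after the first open-label dose, apart from the open-label baseline.
- The repair in SAP 6.13.3 and 6.13.4 covers only the reverse case, post-dose values that fall in the Week 52 window, and only for the summaries of potentially clinically significant (PCS) values.
- The summary in SAP 6.13.3 running from Baseline to Week 104 (hemoglobin, neutrophils, ALT, AST) shows Weeks 52, 78 and 104 but not Week 56, so neither label brings the value into it.

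**5. Where the values do appear.** They are in the listings. For a subject still on drug they can be the last available on-treatment value (SAP 5.12.3, 5.12.4), which is also the fallback in the G6PD and hemoglobin analysis. They count in any-post-Baseline PCS summaries. They can be the open-label baseline (SAP 6.13.3, 6.13.4). For subjects randomized to HMTM, laboratory values enter the HMTM-phase Week 52 window.

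**6. Size.** The documents do not give the share of Week 52 visits held on Days 380 to 456. For illustration only, take 200 per arm and 20% withdrawal (SAP 5.3), so 200 × 0.80 = 160 attending, and assume that late attenders have no other safety value in Days 320 to 379:

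| Assumed late share | In the Week 52 safety row | In the Week 52 efficacy row |
|---|---|---|
| 5% | 160 × 0.95 = 152 | 160 |
| 10% | 160 × 0.90 = 144 | 160 |
| 20% | 160 × 0.80 = 128 | 160 |

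**The case against.** **The limits are deliberate.** Both follow the midpoint to the next scheduled visit, and only safety has a Week 56 visit. That explains Day 379 but does not close the gap. Phase is already separated by the first-dose date, and SAP Table 3 schedules laboratory, vital-sign and examination assessments at Visit 8 for UK sites only. Elsewhere the cut-off makes room for a telephone contact that has no such data.

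**Permission for late visits is unclear.** The SAP 2.5 sentence continues with a condition about two planned visits and shared analysis windows, and its negatives do not resolve. If it means that no two visits may share a window, a Visit 7 after Day 379 would clash with the Week 56 safety window. This stands: a reader might infer that visits up to Day 456 were plainly permitted, and the text does not establish that. The mapping gap exists on either reading.

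**The loss is easily overstated.** A reader might infer that the values vanish, that they are barred from the open-label analysis, or that the Week 52 safety tables hold only on-time attenders. None of these is supported. Step 5 lists where the values survive, the open-label baseline is an express exception in SAP 6.6, and the safety window opens at Day 320, before the protocol window. Nor does SAP 5.12.3 say that the shift tables are specific to Week 52.

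**The eye examination.** A reader might infer that lens discoloration, an adverse event of special interest, would be counted in the wrong phase. That does not follow: such events are recorded as adverse events (Protocol 16.11.2) and tabulated from a list of identified events (SAP 5.12.2). Only the slit-lamp summary by phase in SAP 5.12.6 depends on the Day 379 cut-off. The sentence follows the imaging exception, so it can be read either as an extra allowance for exams after open-label dosing or as a hard limit. It is ambiguous for a pre-dose exam on Day 400, and no more than that.

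**Conclusion.** The gap is real and narrow. Under Table 5 as written, laboratory, vital-sign and examination values taken on Days 380 to 456 before open-label dosing are double-blind data with no visit row. They are missing from the Week 52 rows and plots of the by-visit safety tables, although efficacy scores from the same visit are counted at Week 52. This follows from the text alone and needs no assumption. How many subjects it touches is unknown; the counts in step 6 rest on assumed late shares.

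The affected summaries are descriptive. No efficacy test, significance level or adverse-event tabulation depends on them, and no safety conclusion has been shown to change. It is worth correcting because the omission would be silent and the remedy is small.

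**What to change.** - **Table 5:** keep 320 to 379 for safety. Add that an assessment on Days 380 to 456, taken before the first open-label dose or pre-dose on that day, is assigned to Week 52 if it belongs to the Week 52 visit or if the subject has no value in Days 320 to 379. State how the rule applies to subjects who never take open-label drug.
- **Table 9:** restrict Week 56 to assessments after the first open-label dose.
- **Eye examination (SAP 1.6, 5.5, 5.12, 6.6):** state that a slit-lamp exam before the first open-label dose counts as double-blind even after Day 379.
- **SAP 2.5:** reword the condition on extended windows, and report the number of Week 52 visits held after Day 379 by arm.

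Simply widening the safety window to Day 456 is less good. Within a window, safety uses the worst value, whereas efficacy uses the value closest to the scheduled day. Widening would lengthen the span from 379 − 320 + 1 = 60 days to 456 − 320 + 1 = 137 days over which the worst value is picked. The conditions above limit this effect but do not remove it.

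The cost is table wording, one change to the windowing program and slightly wider timing of Week 52 safety values. Values from Day 457 on stay without a row, as they do for efficacy. SAP 1.6 already provides for re-running the double-blind analysis on the final database lock. SAP Section 10 records that part of the study team was unblinded before version 3.0, so the change should be logged as made after that point.

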**Table 5 Evaluation Intervals for Safety and Efficacy Analyses of the Double-Blind Phase**

Evaluation (scheduled day)	Protocol-Specified Interval	Intervals for Analysis		
		Safety assessments	ADAS-cog13, ADCS-ADL23, MRI	F-FDG-PET, MMSE, CDR
Baseline (1) a	-1 to 1	≤1	≤1	1
Week 4 (29)	26 to 32 [±3]	2 to 67	-	-
Week 13 (92)	78 to 106 [±14]	68 to 137	2 to 137	-
Week 26 (183)	169 to 197 [±14]	138 to 228	138 to 228	-
Week 39 (274)	260 to 288 [±14]	229 to 319	229 to 319	-
Week 52 (365)	351 to 379 [±14]	320 to 379	320 to 456	>1

a Day 1 – first in-clinic dose of study drug

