##### 3.1.1. Double-Blind Populations

**Intention-to-Treat (ITT) Population:** all randomized subjects. Subjects are analyzed as randomized.

**Efficacy Modified Intention-to-Treat (E-MITT) Population:** all ITT subjects who received at least one dose of study drug and have a Baseline and at least one *valid* post-Baseline efficacy assessment (either ADAS-cog11 or ADCS-ADL23). Subjects are analyzed as randomized.

**MRI Imaging Modified Intention-to-Treat (MI-MITT) Population:** all ITT subjects who received at least one dose of study drug and have a Baseline and at least one *valid* post-Baseline volumetric MRI (either whole brain or temporoparietal lobe). Subjects are analyzed as randomized.

**PET Imaging Modified Intention-to-Treat (PI-MITT) Population:** all ITT subjects with screening CDR of 0.5 and who received at least one dose of study drug and have a Baseline and at least one *valid* post-Baseline SUVR assessment (temporal lobe). If data is available from subjects with a CDR > 0.5, these subjects will not be included in this population. Subjects are analyzed as randomized.

**Per Protocol (PP) Population:** all subjects who are in the E-MITT and MI-MITT population, without any important protocol deviation (see Section 3.2) that would deem the subject exclusionary from the PP Population (as per BDRM decision) or intercurrent medical events that could confound the interpretations. Subjects are analyzed as randomized. **Important here refers to a classification that is decided during BDRM based on the original protocol deviation classification as major/minor and their impact on key (efficacy/safety) outcomes of this study. The original classification as major/minor will be provided as well.**

A valid value means that the assessment was not affected by prior initiation of an AChEI and/or memantine.

**Safety Population:** all subjects who received at least one dose of study drug. Subjects are analyzed as treated. If a subject received different doses, the predominant treatment group (based on the number of doses) will be assigned.

**v5-Populations:** If the above-mentioned populations (ITT, E-MITT, MI-MITT, PI-MITT, PP, Safety) are restricted to subjects randomized under study protocol version 5.0 or higher, which are the primary efficacy analysis populations, the population names are: ITTv5, E-MITTv5, MI-MITTv5, PI-MITTv5, PPv5, and Safetyv5.

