#### 5.9.1.5. PET Estimand (ITTv5)

The PET Estimand is designed to answer the question on the treatment effect of HMTM dose of 16 mg/day as monotherapy versus control (containing a small amount of MTC) in the targeted population of subjects with *very mild* AD (CDR of 0.5) at Week 52, regardless of trial product discontinuation, based

Sponsor:	TauRx Therapeutics Ltd.		
Protocol:	TRx-237-039		
Document Version No.:	3.0	Document Date:	07-JUN-2023

on the  $^{18}\text{F}$ -FDG-PET temporal lobe in SUVR. If data is available from subjects with other than a CDR of 0.5, these will not be included in the analysis.

This estimand is constructed in line with ICH E9 (R1) addendum. The five components defining the estimand of interest are:

- A. Treatment:** 52 weeks HMTM dose of 16 mg/day or matching control (containing a small amount of MTC) as monotherapy, regardless of adherence.
- B. Population:** Subjects with very mild AD (CDR of 0.5) and as further described by the inclusion and exclusion criteria, randomized under protocol version 5.0 or higher.
- C. Patient-level outcome / variable:** Change from Baseline of the  $^{18}\text{F}$ -FDG-PET temporal lobe in SUVR at Week 52.
- D. Population-level summary:** Population weighted least squares means difference.
- E. Intercurrent Events:** Identification of ICE is as described for the primary estimand (see Section 5.9.1.1).  
**Events 1** will be handled according to a hypothetical strategy as if patients have stayed on treatment.  
In a sensitivity analysis all these subject withdrawals are assumed to be potentially treatment-related, which are then handled using the treatment policy approach from ICE #2.  
**Events 2** will be handled using a treatment policy approach assuming that the subjects withdrawing from treatment for treatment-related reasons do not retain any treatment effect after Baseline; the intervention effect / in this case is  $I=E*(1-w)$ , where  $E$  is the treatment effect at Week 52 and  $w$  is the fraction of subjects within the HMTM treatment group who withdraw for potentially treatment-related reasons up to Week 52.  
**Events 3** will be handled according to the original randomized treatment group assuming they did not start AChEI and/or memantine and will be analyzed the same as ICE #2.  

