#### MITT population analysis

Data will be analyzed based on the PI-MITTv5 population (see Section 3.1.1), using an ANCOVA, including the randomization stratification variables (see Section 2.6) as fixed factors, the respective efficacy Baseline value as covariate, and the treatment indicator; with the Kenward and Roger method used for calculating the denominator degrees of freedom for the tests of fixed effects.

Sample SAS code (will be fully validated at the analysis stage):

```

PROC MIXED DATA=dataset METHOD=REML COVTEST;
  CLASS subject treatment(REF='Control') severity(REF='moderate') region(REF='Europe')
  prioruse(REF='None');
  MODEL scorediff = treatment severity region prioruse scorebl / SOLUTION CL
  DDFM=KENWARDROGER;
  LSMEANS treatment / CL;
  LSMESTIMATE treatment "intervention effect" 1 -1 / CL;
  RUN;

```

Supplementary and sensitivity analysis will be performed as described in Section 5.9.2.1, except the model-based sensitivity analysis involving the time.

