#### Estimand analysis

The PET estimand (see Section 5.9.1.5) will be estimated using the ANCOVA as described previously for the MITT population.

Sample SAS code (will be fully validated at the analysis stage):

```

PROC MIXED DATA=dataset METHOD=REML COVTEST;
  CLASS subject treatment(REF='Control') severity(REF='moderate') region(REF='Europe')
  prioruse(REF='None');
  MODEL scorediff = treatment severity region prioruse scorebl / SOLUTION CL
  DDFM=KENWARDROGER;
  LSMEANS treatment / CL;
  LSMESTIMATE treatment "intervention effect" nw52 -nw52 / DIVISOR=Nhmtm CL;
  RUN;

```

Sponsor:	TauRx Therapeutics Ltd.		
Protocol:	TRx-237-039		
Document Version No.:	3.0	Document Date:	07-JUN-2023

With  $nw$  the total number of subjects who withdrew for potentially treatment-related reasons during the study until Week 52 in the respective HMTM group and  $Nhmtm$  the total sample size in the HMTM group, then  $nw52 = Nhmtm - nw$ . The numbers will need to be calculated before applying the analyses model (for example saved in macro variables).

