#### 5.9.4. Responder Analysis (Sensitivity)

This analysis is based on the ITTv5 population and is done separately for each of the five primary / secondary efficacy variables (ADAS-cog11, ADCS-ADL23, MRI whole brain, MRI temporoparietal lobe, and  $^{18}\text{F}$ -FDG-PET temporal lobe) and the exploratory efficacy variable Composite Scale, and furthermore separately for each HMTM group comparison versus control.

A responder will be defined as a subject whose change from Baseline to Week 52 is less or equal to a threshold  $T$  (if a larger value means greater impairment, otherwise: *more or equal*), which will be calculated based on the least squares means from the primary analysis model (in Section 5.9.2.1, including all three treatment groups together) and the respective MITTv5 population (E-MITTv5, MI-MITTv5, PI-MITTv5).

$T$  is defined as follows, with  $\text{LSM}_C$  and  $\text{LSM}_T$  the LSM change from Baseline at Week 52 in the control arm and (HMTM) treated arm, respectively:  $T = (\text{LSM}_C + \text{LSM}_T)/2$ .

Subjects who do not have a final assessment at Week 52 will be classified as non-responders. Subjects with no Baseline assessment will not be included in the analysis and counted as missing.

According to the study protocol, the proportion of responders will be analyzed using the Cochran-Mantel-Haenszel (CMH) test, adjusting for the randomization strata variables separately (severity, prior use of standard AD treatment, and region). In addition, the CMH test will be performed adjusting for the prior use of standard AD treatment stopped before Screening. Odds ratios and 95% confidence intervals will be presented.

Sample SAS code (will be fully validated at the analysis stage):

```

PROC LOGISTIC DATA=dataset;
  CLASS treatment(REF='Control');
  MODEL response=treatment;
  STRATA (rand)stratum;
  EXACT treatment;
  RUN;

```

As a sensitivity analysis a logistic regression will be applied to include the randomization strata variables simultaneously (without prior use of standard AD treatment stopped before Screening):

Sponsor:	TauRx Therapeutics Ltd.		
Protocol:	TRx-237-039		
Document Version No.:	3.0	Document Date:	07-JUN-2023

```
PROC LOGISTIC DATA=dataset;  
  CLASS treatment(REF='Control') severity(REF='moderate') region(REF='Europe')  
  prioruse(REF='None');
```

```
  MODEL response=treatment severity region prioruse;  
  RUN;
```

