**Table 9 Evaluation Intervals of the Open-Label Treatment Phase**

Evaluation (scheduled day)	Protocol-Specified Interval	Intervals for Analysis		
		Safety assessments	ADAS-cog 13 , ADCS-ADL 23 , MRI	MMSE, CDR
Week 52 (365) a	351 to 379 [ $\pm 14$ ]	320 to 379	320 to 456	320 to 548
Open-Label Week 56 (394)	380 to 408 [ $\pm 14$ ]	380 to 470	-	-
Open-Label Week 78 (548)	534 to 562 [ $\pm 14$ ]	471 to 638	457 to 638	-
Open-Label Week 104 (730)	716 to 744 [ $\pm 14$ ]	$\geq 639$	$\geq 639$	$> 548$

a Baseline visit for open-label treatment phase

Sponsor:	TauRx Therapeutics Ltd.		
Protocol:	TRx-237-039		
Document Version No.:	3.0	Document Date:	07-JUN-2023

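### SAP Table 5 files every FDG-PET, MMSE and CDR value after Day 1 under Week 52, so a leaver's early-termination PET scan enters the PI-MITT ANCOVA as a 52-week change

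*SAP*

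**What the plan says.** SAP 5.5 states that "all data will be (re-)assigned to a visit according to the column" of analysis intervals in Table 5. The Week 52 row of that table is "Week 52 (365) 351 to 379 [±14] 320 to 379 320 to 456 >1". Its last three entries are the windows for safety data, for ADAS-cog/ADCS-ADL/MRI, and for FDG-PET/MMSE/CDR. The third group has no other post-baseline window. SAP 5.5 limits late values: PET and MRI up to 14 days after the first open-label dose, other efficacy data up to the day of that dose. If a window holds several efficacy values, the one nearest the scheduled day is used.

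Early PET scans are expected. Protocol 15.3.3.1 requires one at early termination when the previous scan is at least 30 days old, and SAP 2.9.1.2 lists the variable at Screening and at 52 weeks or early termination. PI-MITT entry (SAP 3.1.1) needs one valid post-baseline SUVR. Validity excludes only values after an AChEI or memantine was started; there is no minimum time on study.

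The PET model (SAP 5.9.3.2) is an ANCOVA with the stratification factors, "the respective efficacy Baseline value as covariate, and the treatment indicator". The PET estimand "will be estimated using the ANCOVA as described previously for the MITT population", and its variable is the change in "temporal lobe in SUVR at Week 52" (SAP 5.9.1.5). The responder section (SAP 5.9.4) says: "Subjects who do not have a final assessment at Week 52 will be classified as non-responders".

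**The concern.** PET temporal lobe is the second step (16 mg/day) and third step (8 mg/day) of the secondary sequence in SAP 5.9.3, subject to enough subjects providing data (Protocol 9.2.1). If a scan taken a few months after baseline is labelled Week 52, the reported Week 52 effect averages full-year changes with shorter ones, and nothing in the model separates them. That can dilute a real effect. If dropout differs between arms, it can also create a difference where there is none.

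The responder rule then works differently for different endpoints. A leaver with only early ADAS-cog values has no Week 52 value and is a non-responder. The same leaver with one early PET scan does have a Week 52 value under Table 5 and, having had less time to decline, may well pass the threshold.

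**Working it through.** **Does the window behave as described?** The ADAS-cog/ADCS-ADL/MRI windows follow the midpoints between scheduled days: (92+183)/2 = 137.5, (183+274)/2 = 228.5, (274+365)/2 = 319.5 and (365+548)/2 = 456.5. These reproduce the printed limits 137/138, 228/229, 319/320 and 456. The PET entry follows no such rule: the midpoint of Day 1 and Day 365 is Day 183. It is a catch-all. An MRI on Day 60, 120 or 200 goes to Week 13, Week 13 and Week 26; a PET scan on any of those days goes to Week 52. The nearest-to-schedule rule cannot help a leaver with only one post-baseline scan.

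**Does the model adjust for time?** No. By contrast, the while-on-treatment estimand for the clinical scales (SAP 5.9.1.3, 5.9.2.2) uses end-of-treatment values openly and adds duration of exposure as a covariate. Multiple imputation (SAP 4.5.2) covers the co-primaries and MRI whole brain volume, not PET.

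**How large could it be?** The documents give only a trial-wide withdrawal rate of 20-25% over 52 weeks (Protocol 17.2, SAP 5.3). The rest is assumed: SUVR change and drug effect are linear in time, leavers decline like stayers, and early scans are spread evenly over Days 2-319.

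- Mean early-scan day = (2+319)/2 = 160.5, and 160.5/365 = 0.440 of the 52-week change. The shortfall per early scan is 0.560.
- With dropout d and a share s of leavers scanned, early scans make up f = d·s / ((1−d) + d·s) of the PET data. Dilution under equal dropout is 0.560·f.

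| s | f (d = 20%, 25%) | Dilution |
|---|---|---|
| 0.25 | 0.059, 0.077 | 3.3%, 4.3% |
| 0.50 | 0.111, 0.143 | 6.2%, 8.0% |
| 1.00 | 0.200, 0.250 | 11.2%, 14.0% |

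Full capture is unlikely, because Protocol 11.4.2 names only safety evaluations for subjects who withdraw.

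**No drug effect, unequal dropout, s = 0.25.** The arm with more leavers looks better by 0.560 × (0.0769 − 0.0588) = 1.0% of the 52-week decline at 25% against 20%, and by 0.560 × (0.0968 − 0.0423) = 3.1% at 30% against 15%.

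**If leavers decline k times as fast as stayers,** the factor 0.560 becomes 1 − 0.440k. At k = 1.5 the s = 0.25 dilution falls to 2.0-2.6%. The factor is zero at k = 1/0.440 = 2.27 and changes sign above that. Lack of efficacy is a listed withdrawal reason (Protocol 11.4.2), so k above 1 is plausible.

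**Responder status, no drug effect, s = 0.25.** The threshold is the average of the two arm means, −(1 − 0.560f) = −0.967 to −0.957 in units of the 52-week decline. Take normal changes with a constant SD of 0.5, 1 or 1.5 times that decline (assumed) and average over Days 2-319. A scanned leaver then passes with probability of about 0.83-0.82, 0.70-0.69 or 0.64-0.63. A stayer passes with probability 0.47-0.49. If early scans did not count as Week 52, the SAP 5.9.4 rule would give the leaver 0.

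**The case against.** The strongest reply is that the window is deliberate. PET, MMSE and CDR have one planned post-baseline assessment, the SAP describes it as Week 52 or early termination, and the schedule (Protocol Table 10-2) pairs Visit 7 with early termination. An analysis limited to scans from Day 320 is complete-case and open to informative dropout, with no imputation behind it. This stands in part: replacing one window with the other is a trade-off, not a plain correction. But the same visit pairing covers ADAS-cog, ADCS-ADL and MRI, which are still windowed by day, and the PET variable is defined at Week 52.

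A reader might infer that the PET estimand counts withdrawal twice, once through early scans in E and again through w in I = E(1−w). The documents do not support that. Protocol 17.4.3 limits the EMA model to scheduled, on-treatment visits, and Protocol 10.1 and SAP 2.3 describe early-termination visits as unscheduled, so such scans read as excluded from E. What remains is that SAP 5.9.3.2 does not repeat the limit for PET. The restriction does not reach the MITT analysis.

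A reader might also take Table 9, whose Week 52 row gives MMSE and CDR the last of the windows "320 to 379 320 to 456 320 to 548", as proof that Table 5 is a slip. It is weak evidence: only subjects who complete 52 weeks enter the open-label phase (SAP 6.1), and a second MMSE/CDR visit at Week 104 forces bounded windows there.

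On size, starting early scans at Day 30 instead of Day 2 lowers the shortfall to 0.522 and the quarter-scanned dilution to 3.1-4.0%, which changes little. The completers analysis for 16 mg/day removes leavers' scans, but it is supplementary, is not run for 8 mg/day (SAP 5.9.3.4), and also drops subjects who stopped drug yet have an in-window scan. The planned listings would identify early scans subject by subject but would not summarise them by arm. The responder analysis is itself only a sensitivity analysis.

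**Conclusion.** The point holds for the PI-MITT PET analysis at both doses, for PET responder status, and for the exploratory MMSE and CDR-SOB analyses that share the window. As written, a leaver's only early scan is analysed as a 52-week change without adjustment for time.

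The true size cannot be derived from the documents. Under the stated assumptions, dilution is about 3-4% with a quarter of leavers scanned and 11-14% with all scanned. Unequal dropout can move the estimate either way, and faster decline among leavers shrinks or reverses these figures. The text does not support a conclusion that the trial's main result is affected, or that the bias favours the drug: the co-primaries use day-bounded windows, and under equal dropout with leavers declining like stayers the error is towards no effect. This should be clarified and checked, because it touches two steps of the secondary sequence and the check is cheap.

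**What to change.** SAP v3.0 was issued after partial unblinding (SAP 10), so the specified MITT analysis should stay, described as the change at Week 52 or early termination. Beside it:

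- Report, labelled post hoc, the PET result for 16 and 8 mg/day restricted to scans from Day 320, with the existing SAP 5.5 upper limits, and say that it is complete-case. Do the same for MMSE and CDR-SOB if they are reported.
- In SAP 5.9.3.2, repeat the Protocol 17.4.3 restriction to scheduled, on-treatment visits for E in the PET estimand.
- In SAP 5.9.4, require a scan from Day 320 for PET responder status, labelled post hoc if the analysis has already been run.
- Tabulate the number and study day of early-termination PET scans by arm.

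The cost is a few sentences, one small table, one extra PET run per dose, and one run each for MMSE, CDR-SOB and PET responder status where reported. The added PET run loses observations: about 6-8% if a quarter of leavers are scanned, and 20-25% if all are (the f values in the table above). It is also exposed to informative dropout, so neither PET result should be read without the other.
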